9.3. Lenalidomide

9.3.1. **Description**

Lenalidomide, a thalidomide analogue, is an immunomodulatory agent with anti-angiogenic and anti-neoplastic properties. The chemical name is 3-(4-amino-1-oxo 1,3-dihydro-2H-isoindol-2-yl) piperidine-2,6-dione. The empirical formula for lenalidomide is C13H13N3O3, and the gram molecular weight is 259.3.

Lenalidomide is off-white to pale-yellow solid powder. It is soluble in organic solvent/ water mixtures, and buffered aqueous solvents. Lenalidomide is more soluble in organic solvents and low pH solutions. Solubility was significantly lower in less acidic buffers, ranging from about 0.4 to 0.5 mg/mL. Lenalidomide has an asymmetric carbon atom and can exist as the optically active forms S(-) and R(+), and is produced as a racemic mixture with a net optical rotation of zero. Lenalidomide is available in 5 mg, 10 mg, 15 mg and 25 mg capsules for PO administration. Each capsule contains lenalidomide as the active ingredient and the following inactive ingredients: lactose anhydrous, microcrystalline cellulose, croscarmellose sodium, and magnesium stearate. The 5 mg and 25 mg capsule shell contains gelatin, titanium dioxide and black ink. The 10 mg capsule shell contains gelatin, FD&C blue #2, yellow iron oxide, titanium dioxide and black ink. The 15 mg capsule shell contains gelatin, FD&C blue #2, titanium dioxide and black ink.

9.3.2. **Supply**

Commercially available REVLIMID® (lenalidomide) capsules are supplied through the Revlimid REMS® program as the drug is approved for indications in this study. Lenalidomide is for PO (oral) administration only.

9.3.3. Storage Conditions

Store lenalidomide at 25°C (77 °F) away from direct sunlight; excursions permitted to 15-30°C (59-86 °F).

9.3.4. Accountability

Bottles of lenalidomide will contain a sufficient number of capsules to last for one cycle of dosing. Sites will be required to record and document subject compliance regarding lenalidomide dosing.

9.3.5. **Prescribing Information**

Lenalidomide will be provided in accordance with the Revlimid REMS® program of Celgene Corporation. Per standard Revlimid REMS® requirements, all physicians who prescribe lenalidomide for research subjects enrolled into this trial must be registered in must comply with all requirements of the Revlimid REMS® program. Prescriptions must be filled within 7 days. Only enough lenalidomide for one cycle of therapy will be supplied to the subject each cycle.

9.3.6. Special Handling Instructions

Females of child-bearing potential should not handle or administer lenalidomide unless they are wearing gloves.

9.4. **Dexamethasone**

Dexamethasone may be given IV or PO

9.4.1. **Description**

Dexamethasone, a synthetic adrenocortical steroid, is a white to practically white, odorless, crystalline powder. It is stable in air. It is practically insoluble in water.

9.4.2. **Formulation**

Dexamethasone is a commercially available PO drug, supplied as 2 and 4 mg tablets.

9.4.3. Storage conditions

Store dexamethasone at controlled room temperature 20 to 25°C (68 to 77°F)

9.4.4. **Accountability**

Sites will be required to record and document subject compliance regarding dexamethasone dosing.

10. STATISTICAL CONSIDERATIONS

10.1. Objectives

10.1.1. Primary Objective

• The primary efficacy endpoint will be the rate of sCR and/or the rate of negative MRD by next generation gene sequencing (NGS) by clonoSEQ (Adaptive Biotechnologies) at the end of 8 cycles among non-transplant candidates and transplant candidates who agreed to defer transplant

10.1.2. Secondary Objectives

- To evaluate the safety and tolerability of elotuzumab in combination with KRd, when administered to subjects with newly diagnosed multiple myeloma
- Rate of MRD by next generation gene sequencing (NGS) by clonoSEQ (Adaptive Biotechnologies) and by multi-color flow cytometry (MFC) at the end of Cycles 4, 8, 12, and 18 (for subjects who are MRD+ at the end of C8 but MRD- at the end of C12), 24 months after C1D1, and yearly after that.
- Estimate time to event, including duration of response (DOR), progression-free survival (PFS), time to progression (TTP), and overall survival (OS).

10.1.3. Exploratory Objectives

- GEP, proteomics, and gene sequencing to evaluate the correlation between treatment outcome and pre-treatment subject profile.
- Immunologic correlative studies including FcyRIIIa V genotype.

10.2. Sample Size Justification & Analysis Plan

A total of 40, non-transplant candidates, and/or transplant candidates who agreed to defer transplant will be enrolled. Since the study does not plan to exclude transplant candidates who do not wish to defer transplant, an additional 15 subjects who discontinue E-KRd treatment and proceed to transplant are planned to be enrolled to generate additional tolerability and toxicity data, which will bring a total number of subjects to be enrolled to 55. Subjects that continue to transplant will be removed from the study and censored at the end of 4 cycles. These subjects will not be followed up or further analyzed

10.2.1. Primary Objective Sample Size Justification

The primary endpoint is the sCR rate and/or the rate of MRD-negativity after 8 cycles of therapy. The rate of sCR for KRd treatment is established as the primary reference endpoint for statistical considerations by robust data (Jakubowiak et al., 2012b) Recognizing that the measurement of sCR has technical challenges when involving elotuzumab – which are anticipated to be resolved by the time it is needed – a co-primary endpoint of MRD-negative status by NGS is included in the primary efficacy assessment. This is based on the close correlation between MRD-negative status and sCR rate established in the ongoing KRd+transplant study (Jakubowiak et al. EHA 2016, Zimmerman et al. ASH 2016, both oral presentations). This primary endpoint incorporates also the new definition of MRD status, which requires sCR to confirm MRD negativity (Kumar et al., 2016). Therefore, an improvement from historical 30% (which is the sCR rate and the estimated MRD-negative rate by NGS in the KRd study without elotuzumab (Jakubowiak, 2016)) to 50% or higher sCR and/or MRD-negative status at the completion of 8 cycles, would be considered promising.

For 40 non-transplant candidates and/or transplant candidates who agreed to defer transplant, we will test the null hypothesis that the sCR and/or negative MRD status by NGS rate after 8 cycles is, \leq 30% against the alternative that it is, \geq 30% using an exact one-sided binomial test at the alpha=0.10 significance level. The null hypothesis will be rejected if 17 or more sCR's and/or MRD-negative's responses are observed (\geq 42.5%). The sample size of n=40 response evaluable subjects provides a little over 85% power if the true sCR and/or negative MRD status rate by NGS is 50%. The sample size is selected to also allow for collection of sufficient data for toxicity and tolerability evaluation of the E-KRd regimen. The frequency of adverse events will be summarized by type, grade, and attribution to the study drugs.

10.2.2. Secondary Objective Sample Size Justification

Since the rate of MRD-negative disease by NGS methodology at the end of 8 cycles is not established at this time, based on the ongoing evaluations, a rate of NGS MRD-negative disease of 50% or higher after 8 cycles will be considered promising. The rate of successful MRD testing at landmark time points (i.e., after cycles 4, 8, 12, 18 –when applicable- 24 months after C1D1, yearly after that, and/or when nCR is suspected), the rate of VGPR or better, and the rate of near complete responses or better will be estimated along with 90% confidence intervals. DOR, PFS, TTP, and OS will be estimated by the Kaplan-Meier method (Kaplan and Meier, 1958). DOR will be defined as the length of the interval from response to disease progression among responders. PFS will be defined as the time from first dose until disease progression or death from any cause. Subjects alive and without progression will be censored as of the date of the last negative exam.

TTP analyses will be similar to PFS except that subjects who die without a prior disease progression will be censored at the time of death. OS will be calculated as the time from first dose until date of death or date last known alive. In addition to the Kaplan-Meier curves, we will estimate the median time to event and 90% confidence intervals using the method of Brookmeyer and Crowley (Brookmeyer and Crowley, 1982). The study population for PFS, TTP, and OS will be all subjects who receive at least one dose of study drug. The study population for DOR will be subjects who have responded to therapy.

Among all 55 subjects enrolled in the trial, including those who proceed to transplant, we will test the hypothesis that the sCR rate at the end of 4 cycles improves from a historical 8% rate to a higher value, using an exact binomial test at the 0.10 one-sided significance level. The total sample size of n=55 subjects will provide 85% power if the true rate is 19%, and the null hypothesis (\leq 8% rate) will be rejected if 8 or more of the 55 subjects respond. However, any subject who undergoes transplant prior to 4 cycles will be excluded, and the corresponding exact binomial test performed on the reduced sample size. (Thus, for example, if 6 subjects undergo transplant prior to 4 cycles, only 7 responders among the 49 would be needed to reject the null hypothesis.)

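### The cycle-4 sCR test is stated for all 55 enrolled subjects but drops those transplanted before 4 cycles; with 6 such leavers its error is 0.094 if leaving is unrelated to response, and at most 0.148 if it is not

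*Combined protocol and SAP*

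**What the plan says.** Section 10.2.2 defines the population of the cycle-4 test as "Among all 55 subjects enrolled in the trial, including those who proceed to transplant". The hypothesis is that the sCR rate "improves from a historical 8% rate to a higher value", tested "using an exact binomial test at the 0.10 one-sided significance level". The null "will be rejected if 8 or more of the 55 subjects respond", and the section claims 85% power at a true rate of 19%.

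The same paragraph then narrows the population: "any subject who undergoes transplant prior to 4 cycles will be excluded, and the corresponding exact binomial test performed on the reduced sample size". Its illustration is that "if 6 subjects undergo transplant prior to 4 cycles, only 7 responders among the 49 would be needed to reject the null hypothesis".

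Three other places bear on this:

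- The Synopsis (Duration of Treatment) sends transplant candidates to stem cell harvest after cycle 4. Sections 1.7 and 10.2 censor subjects who go on to transplant at the end of 4 cycles.
- The Synopsis and Section 1.7 require the intention to go to ASCT to be stated at enrolment, with 15 subjects planned in that category.
- The same two places replace a non-ASCT or deferred-ASCT subject who goes to transplant only if the reason was neither progression nor toxicity.

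**The concern.** Whether a subject counts in this test depends on something that happens after treatment has started. If early transplant is more common among subjects who are doing poorly, the exclusion removes subjects without sCR from the denominator and can lower the number of responders needed.

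The replacement rule for the cycle-8 cohort shows that the authors foresaw transplant following progression or toxicity. The cycle-4 exclusion makes no such distinction. It is also uneven. A subject who stops in cycle 2 for progression stays among the 55 as a non-responder, but drops out of the denominator if transplanted before 4 cycles.

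At stake is the claim that cycle-4 sCR exceeds 8% in the population the section names. Seven responders are a positive result on 49 subjects and a negative one on 55. Changing the replacement rule for the cycle-8 cohort would not touch this, because it belongs to a different test and a different population.

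**Working it through.** **Inputs, all from Section 10.2.2:** null rate 8%, alternative 19%, one-sided level 0.10, n = 55 with cut-off 8, and the example of 6 exclusions with n = 49 and cut-off 7.

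**Formula.** P(X ≥ r | n, p) = Σ over k = r to n of C(n,k) pᵏ(1−p)ⁿ⁻ᵏ. The cut-off is the smallest r for which P(X ≥ r | n, 0.08) ≤ 0.10.

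**Step 1: reproduce the plan.**
- n = 55: P(X ≥ 7) = 0.148, too large; P(X ≥ 8) = 0.070. The cut-off is 8, and power at 19% is 0.845. This matches the stated 85%.
- n = 49: P(X ≥ 6) = 0.195, too large; P(X ≥ 7) = 0.094. The cut-off is 7, and power at 19% is 0.848. This matches the example.

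**Step 2: when does the exclusion change the cut-off?** The cut-off is 8 for n = 50 to 55 and 7 for n = 41 to 49. With 1 to 5 leavers nothing moves. Six is the smallest number that lowers the bar, and it is the number in the plan's example.

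**Step 3: the same data under both denominators.** Seven responders on 49 give 14.3% and p = 0.094. Seven on 55 give 12.7% and p = 0.148.

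**Step 4: error at 6 leavers.** Assume the 8% null holds over all 55, the population the section names.
- Upper bound: all six leavers come from subjects without sCR. The test rejects when at least 7 of the 55 are in sCR, so the error is P(X ≥ 7 | 55, 0.08) = 0.148.
- Intermediate cases: give leavers an sCR rate q. An overall 8% means 0.08 × 55 = 4.4 expected responders, so the stayers' rate is (4.4 − 6q)/49 and the error is P(X ≥ 7 | 49, that rate).

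| Leavers' rate q | Stayers' rate | Error |
|---|---|---|
| 0% | 8.98% | 0.147 |
| 2% | 8.73% | 0.132 |
| 4% | 8.49% | 0.119 |
| 6% | 8.24% | 0.106 |
| 8% (unrelated to response) | 8.00% | 0.094 |

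The q = 0 row (0.147) and the upper bound (0.148) differ slightly. The first fixes who leaves in advance; the second draws the leavers from those observed without sCR. If leavers are likelier than stayers to be in sCR, the error falls below 0.094.

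**Step 5: error at 0 to 5 leavers.** The cut-off is 8, so the error is at most P(X ≥ 8 | 55, 0.08) = 0.070.

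**Step 6: cost of keeping leavers in.** With 6 leavers counted as not in sCR and a 19% rate in the other 49, the power of the 8-responder cut-off is P(X ≥ 8 | 49, 0.19) = 0.738. The plan's rule gives P(X ≥ 7 | 49, 0.19) = 0.848.

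**The case against.** The exclusion is prespecified, confined to one named event, and paired with a correctly re-derived exact cut-off. If early transplant is unrelated to response, it keeps the error under 0.10. No passage says that early transplant follows poor response, and for the ASCT-intended subjects transplant is a choice declared at enrolment. A subject transplanted before the landmark is unobserved there, so scoring that subject as not in sCR is a convention. The documents also do not say how the historical 8% handled early leavers. If it was computed among subjects completing 4 cycles, the reduced denominator would be the matching one. Finally, cycle-4 sCR is not listed among the secondary objectives or endpoints (Sections 2.2, 3.2, 10.1.2), and no stated decision depends on it.

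Most of this stands, and it limits the point to a modest one. It does not remove it. The section names all 55 as its population, the exclusion applies whatever the reason for transplant, and nothing in the plan shows what the result would be with the leavers kept in.

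A reader might extend the calculation to all 15 planned transplant subjects leaving early, which would lower the cut-off further. The documents do not support that case: harvest comes after cycle 4 and transplant subjects are censored at the end of 4 cycles, so transplant before 4 cycles is off the planned route.

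**Conclusion.** The population stated for the cycle-4 test and the population analysed differ by a post-enrolment exclusion that may be related to response. At 6 leavers the error is 0.094 if leaving is unrelated to response. It lies between 0.094 and 0.148 if leavers are less likely than stayers to be in sCR. At 0 to 5 leavers it is at most 0.070.

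Two stronger conclusions are tempting and do not follow. One is that the plan's example has an error of 0.148. That figure is a ceiling: it needs every leaver to be without sCR and the 8% null to apply to all 55, and the example says nothing about the leavers' response. The other is that the section contains a calculation error; its figures all reproduce.

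The expected number of early transplants is not given, and six is only an illustration. Since early transplants should be few, this is a cheap improvement to a secondary analysis.

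**What to change.** In Section 10.2.2, make the main cycle-4 analysis the one on all treated subjects. Count anyone without a cycle-4 sCR, including those transplanted before 4 cycles, as not in sCR. Take the exact cut-off from the number actually treated (8 if that is 55). Keep the reduced-n test, such as 7 of 49, as a labelled sensitivity analysis on subjects not transplanted before 4 cycles. An all-treated population is already used in the same section for PFS, TTP and OS.

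The cost is a change of about one sentence, with no change to procedures. If 55 are treated, the cut-off is the same under both rules with 1 to 5 leavers. With 6 leavers and a 19% rate in the other 49, power is 73.8% instead of 84.8%. The analysis is conservative if leavers were in fact responding, and the sensitivity analysis would help to show that. In return, with 55 treated and an 8% rate over all of them, the error stays at or below 0.070 whatever the reasons for leaving.

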10.2.3. Exploratory Objectives

The association of exploratory biomarkers (GEP, proteomics, gene sequencing, and immunologic correlates) with outcomes will be analyzed using logistic regression for binary outcomes and Cox regression modeling for time-to-event endpoints (Cox, 1972).

11. DATA REPORTING

Data reporting will be performed utilizing the eVelos electronic data capture system for all subjects. The University of Chicago CRA will provide the applicable user registration information for all sub-sites.

All required data must be recorded in the eVelos database within two weeks of the completion of each cycle. AEs and SAEs are to be entered in eVelos in real time. SAEs are also to be recorded on the paper Serious Adverse Event Form within 24 hours of the site's knowledge of the event and sent via email (preferred) or fax to the University of Chicago ([contact] or [contact]; [contact]).

All case report forms must be completed by designated study personnel. Each screened subject (signed informed consent) is to be entered into eVelos within 48 hours of subject registration. In addition to direct data entry, providing supporting documentation is required as per Subject Enrollment and Registration policies. Source records are original documents, data, and records (e.g., medical records, raw data collection forms, pharmacy dispensing records, recorded data from automated instruments, laboratory data) that are relevant to the clinical trial. Each site will prepare and maintain adequate and accurate source documents. These documents are designed to record all observations and other pertinent data for each subject enrolled in this clinical trial. Source records must be adequate to reconstruct all data transcribed onto the case report form.

12. REGULATORY OBLIGATIONS

12.1.Informed Consent

No Investigator may involve a human being as a subject in research unless the Investigator has obtained the legally effective informed consent of the subject or the subject's legally authorized representative. An Investigator shall seek such consent only under circumstances that provide the prospective subject or the subject's legally authorized representative sufficient opportunity to consider whether or not to participate, and that minimize the possibility of coercion or undue influence. The information that is given to the subject or the representative shall be in a language understandable to the subject or representative.

The Lead PI will provide all Site Investigators with an Informed Consent Form (ICF) developed by the Lead PI. Local and/or institutional requirements may require disclosure of additional information in the ICF. Any changes to this document must be submitted to the University of Chicago CCTO for approval, prior to submission to the participating site IRB. The IRB will review the Informed Consent Form for approval. A copy of the IRB approval form must be submitted to the University of Chicago CCTO prior to initiation of the study at the participating site.

Before implementing any study procedure, informed consent shall be documented by the use of a written consent form approved by the IRB. A copy of signed ICF will be given to the subject or subject's legally authorized representative. The original signed consent must be maintained by the Site Investigator and available for inspection by the designated Lead Principal Investigator representative at any time.

The consent form will include the following:

- 1. The nature and objectives, potential risks and benefits of the intended study.
- 2. The length of study and the likely follow-up required.
- 3. Alternatives to the proposed study. (This will include available standard and investigational therapies. In addition, subjects will be offered an option of supportive care for therapeutic studies.)
- 4. The name of the Investigator(s) responsible for the protocol.
- 5. The right of the participant to accept or refuse study interventions/interactions and to withdraw from participation at any time.

12.2. Compliance with Laws and Regulations

The study will be conducted in accordance with U.S. Food and Drug Administration (FDA) and International Conference on Harmonization (ICH) Guidelines for Good Clinical Practice (GCP), the Declaration of Helsinki, and applicable local health law and authority, and Institutional Review Board (IRB) requirements.

This study must have the approval of a properly constituted IRB. Before the investigational drug is shipped to the Site Investigator, the Lead Principal Investigator or designee will provide BMS and Amgen with a copy of the IRB approval letter stating that the study protocol and any subsequent amendments and informed consent form have been reviewed and approved.

The Lead Principal Investigator and Site Investigator or designee will be responsible for obtaining annual IRB re-approval throughout the duration of the study, when necessary.

The Lead Principal Investigator and Site Investigator are also responsible for notifying their IRB of any significant adverse events that are serious and unexpected as per their policies.

BMS will provide the Lead Principal Investigator with any expedited safety reports generated from any ongoing studies with elotuzumab, changes to the Investigator's Brochure, and any other safety

information which changes the risk/benefit profile of elotuzumab during the conduct of the study, to allow him/her to fulfill his/her obligation for timely reporting to the IRB, participating sites, and other Investigators participating in the study, when necessary.

Amgen will provide the Lead Principal Investigator with any expedited safety reports generated from any ongoing studies with carfilzomib, changes to the Investigator's Brochure, and any other safety information which changes the risk/benefit profile of carfilzomib during the conduct of the study, to allow him/her to fulfill his/her obligation for timely reporting to the IRB, participating sites, and other Investigators participating in the study, when necessary.

Upon completion of the trial, the Lead Principal Investigator must provide the IRB, BMS and Amgen with a summary of the trial's outcome.

12.3. Subject Confidentiality

Subject medical information obtained as part of this study is confidential, and must not be disclosed to third parties, except as noted below. The subject may request in writing that medical information be given to his/her personal physician.

The Investigator/Institution will permit direct access to source data and documents by the FDA and/or other applicable regulatory authority. The access may consist of trial-related monitoring, audits, IRB reviews, and FDA inspections. Identifiable data will be shared by the following collaborator: Adaptive Biotechnologies (to allow an IDE annual report to FDA).

Release of research results should preserve the privacy of medical information and must be carried out in accordance with the Department of Health and Human Services Standards for Privacy of Individually Identifiable Health Information, 45 CFR 164.508.

